- The following will be reviewed at the DSMB meeting and included in the report which will be compiled following DSMB meetings and then updated at the trial's conclusion: 1) brief description of the trial; 2) baseline sociodemographic characteristics; 3) accrual, retention and disposition of study participants (recruitment versus goal, withdrawal rate); 4) quality control issues (assessment of randomization procedures, including stratification); 5) regulatory issues (review of protocol changes); 6) side effects by treatment arm (overall and by site); 7) serious adverse events by treatment arm (overall and by site); and 8) efficacy.

Structure of DSMB meeting. Each meeting will consist of three parts. First, an open session will occur in which the [name] and the DSMB will review the conduct of the trial (e.g., accrual, protocol compliance, general toxicity). Second, to maintain the study blind, a closed session involving only the DSMB and Dr.

[name], the study biostatistician, will be held during which he will present side effect results to the DSMB as requested. A report of unblinded side effects results will be prepared; however, it will only be presented if specifically requested by the DSMB. This will focus on the presentation of the rate of increase in any side effect from baseline to a follow-up across treatment arms. Finally, an executive session involving only DSMB members will be held to allow the DSMB the opportunity to discuss the conduct of the trial and outcomes, including toxicities and adverse events, develop recommendations, and take votes as needed. The DSMB written recommendations will be provided to [name] and to the IRBs. The DSMB will summarize AE reports for [name] and the IRB chair, and [name] must implement any DSMB recommendations expeditiously. All DSMB recommendations will also be forwarded to the NIH and the FDA (where necessary).

RETAIN Sub-Study DSMB.

Ongoing oversight of the RETAIN sub-study is provided by a DSMB committee, whose members are: [name] (Chair, Associate Professor of Medicine and Medical Ethics, Baylor College of Medicine), [name] (Associate Professor, Department of Radiation Oncology, Robert Wood Johnson Medical School, Rutgers Cancer Institute of New Jersey), [name] (Research Associate Professor, Biostatistics, University of Pittsburgh, Graduate School Public Health), [name], MPH (Associate Professor, Medicine, Harvard Medical School), and [name] (Patient Advocate).

The RETAIN PI ([name]), assisted by the PENN project manager ([name]), will be responsible for maintaining communication between the DSMB and the individual project staff for all RETAIN-related activities. The DSMB will be responsible for monitoring the trial and making decisions about the termination of individual study arms or the study itself. The DSMB will review and approve the research protocol. They will also assess the progress of the trial, including the assessment of data quality, participant recruitment, accrual and retention, participant risk versus benefit, and study outcomes.

Data Management System (DMS)

The Northwestern database manager will oversee the DMS for this trial and direct the Northwestern DMS to link with PENN. MS ACCESS permits real-time data entry, storage, and QA by NU secured network remote access and scannable forms, which increase standardization across personnel. This system is being used in our ongoing varenicline trial of smokers with cancer (R01CA165001/**STU00064871**). The DMS generates database tables in a NIH-compliant format, constructs semantic constraints on fields, and is used for data entry, storage, retrieval, and security. The DMS uses session dates to describe procedures and measures to be ascertained. The DMS mimics the appearance of CRFs completed at sessions. During data entry, validation occurs via the following procedures: 1) Variable type checks - variables defined as specific type, e.g., integer, and entry is restricted to type; 2) Range checks - entry of data outside a range is rejected; 3) List of possible values checks - value of data is checked against acceptable values; 4) Internal logical consistency checks - dependent fields are logical (e.g., study entry date occurs after birth date); 5) Data completeness checks - data inspected for completeness; and 6) Duplicate record checks - data are inspected to prevent duplication. Daily backups occur to protect against accidental corruption or deletion. We compare 100% of hard copy to computer data. Protection of participant privacy is accomplished by minimizing use of identifying information, use of ID numbers rather than participant names, keeping all data in locked files, and limiting access to the dataset that links participant names with ID numbers strictly to the study biostatistician.

RETAIN Sub-Study Data Management

All RETAIN survey data will be managed in REDCap (Research Electronic Data Capture), a secure data management system available at both PENN and NU. Questionnaire measures will either be entered into REDCap directly by participants (i.e., at the in-person intake session), or completed via pen and paper questionnaires and entered into REDCap by study staff. The RETAIN Project Data Managers will maintain the database with oversight from key study personnel.

All datasets and computer files and study ID numbers will be further secured as follows. We will implement multiple, redundant protective measures to guarantee the security of participant data. All data for this project will be stored on the secure/firewalled servers of the Center for Clinical Epidemiology and Biostatistics (CCEB). These data servers are maintained in a guarded facility behind several locked doors, with very limited physical access rights. They are also cyber-protected by extensive firewalls and multiple layers of communication encryption. Electronic access rights are carefully controlled by Penn system managers. We will use highly secure methods of data encryption for all transactions involving participants' financial information, such as W-9 forms, using a level of security comparable to what is used in commercial financial transactions. This multi-layer system of data security, identical to the system protecting the University of Pennsylvania Health System's medical records, greatly minimizes privacy risks.

Only authorized personnel will have access to the data. All of these personnel will have completed research and confidentiality training (specifically, CITI training). Through REDCap, each study subject will be given a

unique study identification number (ID). By default, all direct identifiers will be omitted from data extracts, and the study ID will be used exclusively in all analytical files.

STATISTICAL CONSIDERATIONS

Power

To address hypotheses related to Aims 1-3, we base our estimates upon the Anthenelli et al. trial (2013) and the study by MacPherson et al (2010) that randomized 68 smokers with elevated depressive symptoms (BDI-II scores ≥ 10) but no current MDD to 8 weeks of treatment with either behavioral activation (BA) or standard behavioral treatment (BT). At 26-weeks post-TQD, bioverified 7-day point-prevalence abstinence rates were 14.3% for BA (n=35) and 0% for BT (n=33). In the Anthenelli et al. trial (2013), smokers with current or past (≤ 2 years) MDD received 12 weeks of varenicline or placebo. Bioverified 7-day point-prevalence abstinence rates at 24 weeks were 31.3% for varenicline (n=256) and 18.2% for placebo (n=269). Based upon our conceptual model of the therapeutic targets of BASC and varenicline individually, we predict that there will be a synergistic effect of combination treatment with BASC and varenicline on abstinence (see Figure 2). Assumed 7-day point prevalence abstinence rates at 24-weeks post-TQD in our 2x2 design are presented in Table 3, under an ITT approach that considers participants lost to follow-up as treatment failures. A minimum of N=128 participants be assigned to each psychological treatment group (BASC, ST) receiving placebo, while a minimum of N=160 participants be assigned to each psychological treatment group (BASC, ST) receiving varenicline.

Such a sample configuration (N=576 total) guarantees at least 85% power for testing each of the three pairwise comparisons of interest in Primary Aim 3: BASC + varenicline vs. ST + varenicline (42% vs. 24% abstinence, power = 85%), BASC + varenicline vs. BASC + placebo (42% vs. 18% abstinence, power = 98%), and BASC + varenicline vs. ST + placebo (42% vs. 5% abstinence, power > 99%) at a multiplicity-adjusted significance level $\alpha = .053 = .0167$.

This equates to enrolling about 12 participants per month (6/month/site) over the 48 month recruitment period. Further, it guarantees 91% power for testing the efficacy of BASC vs. ST (18% vs. 5% abstinence) among the

		Psychological Treatment	
		ST	BASC
Pharmacological Treatment	Placebo	5%	18%
	Varenicline	24%	42%

N=256 participants receiving placebo (Primary Aim 1), and power in excess of 99% for testing the efficacy of varenicline vs. placebo (24% vs. 5% abstinence) among the N=288 participants receiving ST (Primary Aim 2) when the significance level for these tests is fixed at $\alpha = 0.05$. Aim 2a will be tested based on a non-inferiority approach that seeks to establish the maximum increase in the moderate-to-severe AE rates (individual, total) in the varenicline arm relative to that in the placebo arm consistent with rejecting at $\alpha = .05$ the one-sided null hypothesis that the true varenicline vs. placebo AE Rate Ratio (RR) exceeds 1.25 (Hauschke, Kieser, Diletti, & Burke, 1999). Assuming a 67% AE rate in the placebo arm, we have 84% power to establish non-inferiority, provided that the AE rate in the varenicline arm does not exceed 72%. That is, we need a true RR < 1.075 (72% vs. 67%) to have an 84% chance of observing a sample RR small enough to lead to a rejection at $\alpha = .05$ of the null hypothesis that the true RR > 1.25.

Regarding Secondary Aim 1 (Mediation), Fritz and MacKinnon (2007) present sample size requirements for a variety of mediation scenarios, assuming a continuous mediator (e.g., change in hedonic capacity) and a continuous dependent variable (e.g., change in cigarette reward value). With the exception of a rather unlikely complete mediation scenario, under which the entire effect of treatment assignment occurs through differences in hedonic capacity, the sample size required for 80% power at the 5% significance level was N=562 provided that 1) the main effect of treatment assignment on hedonic capacity, and 2) the effect of hedonic capacity on cigarette reward value each explain only 2% of the variance in the respective normal regression models, corresponding to “small” effects in Cohen’s nomenclature (Frandsen, Walters, & Ferguson, 2014). This is below N=576, suggesting adequate power for detecting mediation of proximal continuous outcomes. For the more distal outcome of abstinence (yes/no), the Fritz & MacKinnon (2007) method can still be used, provided our effective sample size is adjusted downwards to reflect loss of information due to dichotomization (Gibbons & Mann, 2013). Results suggests that detecting mediation of treatment effects on abstinence rates will be more

challenging, and will require effects of changes in cigarette reward value on smoking abstinence to be in the “medium-to-large” range instead.

Data Analysis

Preliminary analyses will assess sample characteristics by treatment with chi-square or logistic regression (tobacco dependence, use of antidepressant medication, number of past depressive episodes, and number of other Axis I disorders). These variables will also be examined for their relationship to completion of outcome assessments. Variables related to treatment arm and completion of follow-ups will be included as covariates in analyses of study aims. Treatment compliance measures (psychological treatment sessions, medication) will be evaluated across treatment arms, and controlled for in primary analyses.

Primary Aims 1-3: Outcome Analyses

[figure not shown]
The primary outcomes will be 7-day point prevalence abstinence at week 27 (24-weeks post-TQD; self-reported abstinence for 7 days prior to the assessment and breath CO \leq 8 ppm) and AE rates. CO-verified 7-day point prevalence abstinence at weeks 7 and 14 (4- and 10-weeks post-TQD, respectively) will be secondary measures. As per guidelines (Hughes et al., 2003), secondary outcomes at 24-weeks post-TQD will include: prolonged abstinence (relapse defined as 7 consecutive days of self-reported smoking after a 2-week grace period), continuous abstinence (no smoking between TQD and follow-up), and time to 7-day relapse. Other than time to relapse, all outcomes of interest are binary (abstinence and AE rates) and will be analyzed using logistic regression. The effect of varenicline on AE rates (Primary Aim 2a) will be based upon the union-intersection test arm for establishing non-inferiority in the proportion of participants experiencing moderate to severe AEs in the varenicline vs. the placebo arm (Hauschke et al., 1999). To ensure that tests on the overall sample do not mask differential effects by antidepressant medication use and type, these analyses will be preceded by a Breslow-Day for homogeneity across strata of interest. If no evidence of heterogeneity is found, stratum-specific estimates will be combined using a Cochran-Mantel-Haenszel weighing scheme (Wiens & Heyse, 2003).

Missing Data Approaches

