7. If women of childbearing potential, based on medical history and regardless of sexual orientation, consent to use a medically acceptable method of birth control (e.g., condoms, oral contraceptive, contraceptive injection, contraceptive patch, tubal ligation) or abstain from sexual intercourse during the time they are taking study medication and for at least one month after the medication period ends.

Key Exclusion Criteria

Participants who present or self-report any of the following will not be eligible to participate in the study:

Smoking Behavior

1. Current enrollment or plan to enroll in another smoking cessation program in the next 8 months.
2. Regular (daily) use of e-cigarettes, chewing tobacco, snuff, snus, or other tobacco product.
3. Plan to use nicotine replacement therapy (NRT; e.g., gum, patch, lozenge, e-cigarette) or other smoking cessation pharmacotherapy in the next 8 months.

Note: Once determined to be eligible for the study, participants will be instructed to refrain from using non-study smoking cessation pharmacotherapy for the duration of the study. However, if a participant reports cessation medication use during the study, s/he may be permitted to continue pending study physician and PI approval.

Medication

Current use or recent discontinuation (within last 14 days) of the following medications:

1. Smoking cessation medications (e.g. varenicline, bupropion - if prescribed specifically for smoking cessation - nortriptyline, NRT).

Note: Once determined to be eligible for the study, participants will be instructed to only use the medication provided to them by the study staff. If a participant reports use of a non-study smoking cessation medication, the study physician and PI will evaluate the situation and determine if it is safe for the participant to continue.

2. Medications indicated for bipolar or psychotic disorder if specifically taken for bipolar or psychotic disorder.

Medical

1. Women who are pregnant, planning a pregnancy within the next 8 months, or breast feeding;
2. History of seizures or current seizure disorder without medication (if stable and medicated, requires physician approval).
3. History of severe (defined as stage IV or V) chronic kidney disease including current or prior end stage renal disease on either hemodialysis or peritoneal dialysis or prior renal transplant.
4. Any prior solid organ transplant or prior hematopoietic stem cell transplant.

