5. Heavy drinking as defined by more than 28 drinks per week.
6. Cirrhosis or end-stage liver disease.
7. Systolic blood pressure >185 mmHg or diastolic blood pressure >110 mmHg after two averaged readings or symptomatic uncontrolled stage II hypertension (systolic blood pressure >160 mmHg or diastolic blood pressure > 100 mmHg after two averaged readings with current reported symptoms of chest pain, dyspnea, headache, or blurred vision).
8. Unstable cardiovascular disease within 3 months prior to baseline assessment, including unstable angina, myocardial infarction, percutaneous coronary intervention, transient ischemic attack, stroke, or other cardiovascular disease requiring hospitalization.
9. Prior hospitalization for heart failure.
10. Previous allergic reaction to varenicline.

Psychiatric

1. Active suicidal ideation within the last 30 days with at least some intent to act, with or without a specific plan. This would be reflected in a score of 4 or 5 on the Suicidal Ideation section of the Columbia Suicide Severity Rating Scale (C-SSRS).
2. As measured using the C-SSRS, a suicide attempt over the past 12 months, not including preparatory acts or behavior, defined by a potentially self-injurious act committed with at least some wish to die as a result of the act.
3. Lifetime bipolar or psychotic disorder as determined by either self-report or Mini International Neuropsychiatric Interview (MINI).

General

1. Any medical condition or concomitant medication that could compromise participant safety or treatment, as determined by the PI or study physician.
2. Inability to provide informed consent or complete any of the study tasks (e.g., medical condition with a life expectancy < 1year) as determined by the PI or study physician.

Vulnerable Populations

Children under 18 years of age, pregnant women, fetuses, neonates, or prisoners will not be included in this study. Socioeconomically disadvantaged persons will be included in this study, but not targeted for recruitment. It is possible that Northwestern and PENN employees or students may choose to participate. However, status of participation in the study will be independent of the participant's work or school activities.

Recruitment and Accrual Procedures

Treatment Sites

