All participants will receive manual-based treatment from a therapist trained and supervised by Drs. [name] (Northwestern), [name] (PENN), and [name] (PI). After final eligibility has been confirmed by either the project director, study physician or PI (lead and PENN clinical site), participants will be randomized to receive either the BASC or ST interventions. BASC treatment will integrate behavioral activation therapy (Dimidjian et al., 2011; Jacobson et al., 1996; Lejuez et al., 2001) and ST. ST will be based on the 2008 PHS Clinical Practice Guideline (Fiore, 2008) and on ST in our recently completed and ongoing two-site trials (R01DA025078 and R01CA165001, respectively). BASC and ST will be delivered in eight 45-minute sessions over 12 weeks, weekly for the first four sessions and every other week for the final four sessions. Session frequency and duration are based upon past CBT MM trials (Haas, Munoz, Humfleet, Reus, & Hall, 2004; Patten, Martin, Myers, Calfas, & Williams, 1998). BASC and ST will follow the same schedule, equated on number of sessions and total participant-therapist contact time. The schedule for both psychological treatment arms is described next.

Pre-quit sessions 1 and 2 (Weeks 1 and 2): BASC and ST begin with two "Pre-Quit" therapy sessions (Pre-Quit 1 in-person, Pre-Quit 2 by phone) designed to help participants prepare for the target quit day (TQD/Week 3). These sessions focus on reviewing participant's history and experience with quitting and, per random assignment, will also introduce either the BASC or ST treatment models and participants will initiate a quitting plan that aligns with techniques from the assigned therapeutic approach. Two weeks of medication are dispensed at Pre-Quit 1 and participants will be instructed to wait until the day of Pre-Quit 2 (Week 2) to start

taking the study medication. During the Pre-Quit 2 (Week 2) phone session, participants will be instructed to take their medication starting that day. The therapist will contact participants two days later to ensure that instructions regarding medication use are being followed.

Target quit day session (Week 3): At Week 3, participants will complete their in-person “Quit Day” session to review the initial quit attempt, identify potential reasons for relapse, and review their quit plans. Medication for weeks 3-7 will be dispensed at this visit.

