Blood pressure: At the baseline intake visit study candidates will have two blood pressure readings taken, each after a five-minute period in which the person will be instructed to sit comfortably in a quiet setting. If, after taking the average of the two readings, a candidate has a blood pressure reading above either: (a) 185 mmHg systolic and/or 110 mmHg diastolic, or (b) above 160 mmHg systolic and/or 110 mmHg diastolic with co-occurring symptoms of chest pain, dyspnea, headache, or blurred vision, s/he will be ineligible for the study. Blood pressure will be measured at every clinic visit. If a participant presents with elevated blood pressure ($\geq 185/110$ or $\geq 160/100$ and symptomatic, averaged from two readings) at any clinic visit following the intake session, the study physician will be notified to determine how to proceed. For example, the participant may be discontinued from study medication and invited to continue in the trial to complete psychological treatment and assessments only. Additional study drug will not be given to the participant until cleared by the study physician.

Psychiatric treatment and depression/anxiety symptoms: We will collect information about treatment history, including psychotropic medication, psychotherapy, and hospitalization. Use and type of antidepressant medication will be measured across treatment using a timeline follow-back (TLFB) interview (Brown et al., 1998) and recorded on a depression medication adherence questionnaire. This TLFB interview is the same as what we have used in our completed and ongoing two-site trials involving pharmacotherapy (R01DA025078 and R01CA165001/**STU00064871**, respectively). The depression medication adherence questionnaire also asks about reasons why participants have missed taking their antidepressants. Depression symptoms will be measured using the Beck Depression Inventory (BDI-II) (Beck et al., 1996). The BDI-II yields a total score ranging from 0-63, with scores of 0-13 indicating minimal depression, 14-19 indicating mild depression, 20-28 indicating moderate, and 29-63 indicating severe depression. Anxiety symptoms will be measured using the Beck Anxiety Inventory (BAI) (Beck & Steer, 1990). The BAI also yields a total score ranging from 0-63 points, with scores of 0-7 indicating minimal anxiety, 8-15 indicating mild anxiety, 16-25 indicating moderate anxiety, and 26-63 indicating severe anxiety.

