All serious AEs, as defined in the adverse event procedures in the Safety Monitoring and Reporting Protocol, will be reported within 24 hours to the PIs (lead and PENN PI). These events will be maintained in a unique database and reviewed monthly by senior study personnel. The site physician and psychologists will review all AE forms in “real-time” to ensure appropriateness of the data and timeliness of reporting. The Northwestern database manager and research assistants will be responsible for monitoring data integrity as data are collected. This includes ensuring that source documents exist for the data on the CRFs, ensuring all fields are completed appropriately, all corrections are done according to GCP and any inconsistencies and deviations are documented.

The study will be monitored by the PIs (lead and PENN site), co-investigators, and regulatory committees at Northwestern and PENN as well as by a study-specific DSMB. The following monitoring activities will be conducted according to standard operating procedures.

Initial Assessment Monitoring

The Northwestern database manager and site project directors will conduct a manual review of source documents and CRFs for a random 25% subset of participants enrolled in the study. This inspection is the visual comparison of source documents to CRFs in a quantitative assessment of accuracy based on the number of data fields. A brief, internal report will be generated to describe findings. If the data are less than acceptable (i.e., >1% discrepancy between data values from source documents compared to CRFs), additional cases are requested, with appropriate counseling/training for staff.

Protocol Monitoring

Protocol monitoring includes a survey of those activities that are associated with protocol adherence such as study visit deviation and violation of inclusion/exclusion criteria. All accrued cases will be subjected to protocol monitoring throughout the duration of the trial.

Database Auditing

The Northwestern database manager and research assistants will review data entered into the database versus that recorded on the CRFs. All accrued cases will be subjected to database auditing throughout the duration of the trial. Re-training will be provided should problems, such as increased errors, be detected.

Data Auditing

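### The Measures section sets the symptomatic diastolic exclusion limit at intake to 110 mmHg; the exclusion criteria set it to 100 mmHg

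*Combined protocol and SAP*

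**What the plan says.** The protocol states the intake blood pressure exclusion twice.

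- **Key Exclusion Criteria, Medical item 7.** The limit regardless of symptoms is "Systolic blood pressure >185 mmHg or diastolic blood pressure >110 mmHg after two averaged readings". The symptomatic limit is a systolic above 160 mmHg or "diastolic blood pressure > 100 mmHg after two averaged readings with current reported symptoms", followed by four named symptoms. The list is introduced by "Participants who present or self-report any of the following will not be eligible to participate in the study".
- **Measures, Screening/Covariates, Blood pressure.** This describes how the two readings are taken and averaged at intake. It makes a candidate ineligible above either limb ("a) 185 mmHg systolic and/or 110 mmHg diastolic") or limb (b), "above 160 mmHg systolic and/or 110 mmHg diastolic with co-occurring symptoms of chest pain, dyspnea, headache, or blurred vision".

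The same Blood pressure paragraph then gives a rule for clinic visits after intake. The study physician is notified at 185/110 or above, or at or above "160/100$ and symptomatic, averaged from two readings" (the dollar sign is left over from text extraction).

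**The concern.** Two different diastolic limits, 100 and 110 mmHg, are given for one decision, so at least one is wrong. The Measures section is the text that describes the intake procedure. Staff who screen from it could admit a symptomatic candidate whom Medical item 7 excludes.

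Such an error would be hard to undo. Randomization takes place at the same intake session (Baseline Intake Session, step 10), and the ITT analysis includes everyone randomized (Missing Data Approaches). Enrolling the candidate would also be an eligibility violation, which the Protocol Monitoring section lists among the items it tracks: "such as study visit deviation and violation of inclusion/exclusion criteria".

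The exclusion serves a safety purpose. The protocol gives possible cardiovascular effects of varenicline as its reason for monitoring blood pressure (Side Effect Monitoring), and cardiovascular events are part of Primary Aim 2a.

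**Working it through.** No sample size, power or alpha figure is involved, so the check is a comparison of two decision rules. Let S and D be the averaged systolic and diastolic readings in mmHg, and let Y mean that at least one of the four symptoms is present.

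**The rules**

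- Medical item 7: exclude if S > 185, or D > 110, or (Y and (S > 160 or D > 100)).
- Measures, limbs (a) and (b): exclude if S > 185, or D > 110, or (Y and (S > 160 or D > 110)).

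They differ only in the last number.

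**Does the diastolic part of limb (b) do anything at 110?** It needs Y and D > 110. Any D > 110 is already excluded by limb (a), whether or not Y holds. So it never decides a case, and the Measures rule reduces to: S > 185, or D > 110, or (Y and S > 160).

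**Where the rules disagree**

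- Excluded by Medical item 7 but not by Measures: Y, with 100 < D ≤ 110 and S ≤ 160. In whole mmHg, D runs from 101 to 110.
- Excluded by Measures but not by Medical item 7: none, because D > 110 implies D > 100. The error runs only in the permissive direction.

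**Examples**

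| Averaged reading | Symptoms | Medical item 7 | Measures as written | Measures with 100 in (b) |
|---|---|---|---|---|
| 150/105 | headache | excluded (105 > 100) | not excluded (105 ≤ 110, 150 ≤ 160) | excluded |
| 150/105 | none | not excluded | not excluded | not excluded |
| 165/105 | headache | excluded | excluded (165 > 160) | excluded |
| 150/112 | none | excluded (112 > 110) | excluded by (a) | excluded by (a) |

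**Which number is wrong?** Three things point to the 110 in limb (b):

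1. At 110 the diastolic part of the limb has no function; at 100 it has one.
2. The post-intake rule pairs 185/110 regardless of symptoms with 160/100 when symptomatic, the same two tiers as Medical item 7.
3. Medical item 7 is the formal criterion.

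With 100 in limb (b) the two rules are identical for every combination of S, D and Y. The intake rules use strict inequalities and the post-intake rule uses at or above, but this does not bear on the point.

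**The case against.** The discrepancy itself is hard to dispute; the case on the other side concerns its weight.

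- **The governing rule is correct.** Anyone meeting Medical item 7 is ineligible whatever the Measures section says. This stands: the Measures text is an incomplete restatement of the exclusion and does not create a second enrolment rule.
- **Staff may not screen from the Measures text.** The protocol says they work from a Manual of Operations, case report forms and visit checklists, which are not available here. This also stands, so the consequence is conditional. It is also the reason to check the form.
- **Other safeguards exist.** Randomization comes "After final eligibility has been confirmed by either the project director, study physician or PI"; a general exclusion lets the PI or study physician rule out a candidate on safety grounds; and blood pressure is measured again at Week 1, when medication is first dispensed. These reduce the risk but do not correct the text. The general exclusion is discretionary, and the Week 1 check comes after randomization and works only if the elevated reading and symptoms recur.
- **The post-intake rule is looser support than it looks.** It triggers physician notification, not exclusion, and its slash notation does not say whether both components must be exceeded. Whether 150/105 with headache would trigger it therefore depends on how it is read. It still supports 100 as the intended symptomatic diastolic figure, and the contradiction with Medical item 7 does not depend on it.

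**Conclusion.** The concern holds. Limb (b) of the intake blood pressure rule is wrong as written: its diastolic limit should be 100 mmHg. This is an internal inconsistency in a safety exclusion, not a flaw in the design or the analysis.

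Its reach is narrow: symptomatic candidates with an averaged diastolic above 100 and up to 110 mmHg and a systolic of 160 mmHg or less. How many candidates fall in that band cannot be derived from the documents. Harm arises only if staff or the screening form follow the Measures wording and no later check intervenes. The sample size, power and primary efficacy analysis do not change. The correction should still be made, because the text gives a wrong threshold for a safety decision and the right value already stands elsewhere in the same protocol.

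**What to change.** In the Blood pressure item of the Measures section, limb (b), change the diastolic limit from 110 to 100 mmHg, so that it matches Medical item 7 and the post-intake 160/100 symptomatic rule. Check that the intake screening form uses 100 as well. The cost is one number in the protocol text and one check of the form.
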